8.2 STATISTICAL ANALYSES

8.2.1 Safety Analyses

Safety analyses will be provided in the safety population.

AEs will be presented overall and by period of treatment (Sunitinib, Axitinib).

They will be displayed in summary tables, by system organ class (SOC) and preferred term (PT).

The tables will present the number of subjects and the rate of occurrence within each period for which the events occurred. The rate of occurrence will be expressed as a percentage of the subjects from the Safety Analysis Set receiving the treatment concerned.

For the number of subjects and the rate of occurrence, the same classification (SOC and / or PT) in the same patient is counted only once.

In a first time, an overview of all AEs will be given overall and by period of treatment (Sunitinib, Axitinib) and will include the description of the number and the percentage of patients with the following criteria:

- At least one AE
- At least one SAE
- At least one non-serious AE
- At least one grade 3 AE
- At least one grade 4 AE
- At least one grade 3/4 AE

Same analysis will be repeated on related AEs only.

Then each of the following categories of AEs will be described by SOC and PT overall and by period of treatment (Sunitinib, Axitinib):

PFIZER CONFIDENTIAL

Page 28 of 41

- All AEs
- Most common AEs (SOC or $PT \ge 10\%$)
- SAEs
- Non-serious AEs
- Grade 3 AEs
- Grade 4 AEs
- Grade 3/4 AEs

Same analysis will be repeated on related AEs only.

Proportion of patients who discontinued the treatment of interest because of AEs will be given with its 2-sided 95% 'exact' Clopper-Pearson confidence interval overall and by period of treatment (Sunitinib, Axitinib).

Treatment duration until discontinuation for AEs will be analyzed using descriptive statistics (mean, standard deviation, median and range) overall and by period of treatment (Sunitinib, Axitinib).

Proportion of patients who died due to any cause will be given with its 2-sided 95% 'exact' Clopper-Pearson confidence interval overall and by period of treatment (Sunitinib, Axitinib). Causes of deaths (tumor-related, other cause) will also be described.

8.2.2 Analyses of Efficacy Endpoints

Efficacy analyses will be provided in the FAS population.

Primary endpoints

PFS under Axitinib in 2nd line post Sunitinib will be described using the Kaplan Meier method in the SU-AXI subgroup:

• Kaplan-Meier estimates (product-limit estimates) will be presented with a summary of associated statistics: number of events, number of censored data, median survival time, Q1 and Q3 survival times and survival rates every 3 months.

The confidence intervals for the median, Q1 and Q3 will also be provided according to Brookmeyer and Crowley (1982)

• The Kaplan-Meier curve will also be presented

Other primary endpoints will be analyzed according to the same methods:

- PFS for the sequence Sunitinib-Axitinib in the SU-AXI subgroup
- TTF under Axitinib in 2nd line post Sunitinib in the SU-AXI subgroup
- TTF for the sequence Sunitinib-Axitinib in the SU-AXI subgroup

Additionally a Cox regression model will run for the PFS under Axitinib in 2nd line post Sunitinib in the SU-AXI subgroup according to the method described in section 8.1 of this document (Strategy of selection of variables in multivariate models). Potential factors to be tested will be defined at time of Data Review Meetings among the ones mentioned in section 6.4 of this document.

Secondary endpoints

TSF for the sequence Sunitinib-Axitinib will be described using the Kaplan Meier method in the SU-AXI subgroup:

• Kaplan-Meier estimates (product-limit estimates) will be presented with a summary of associated statistics: number of events, number of censored data, median survival time, Q1 and Q3 survival times and survival rates every 3 months.

The confidence intervals for the median, Q1 and Q3 will also be provided according to Brookmeyer and Crowley (1982)

• The Kaplan-Meier curve will also be presented

Following secondary endpoints will be analyzed according to the same methods:

- OS for the sequence SU-AXI in the SU-AXI subgroup
- PFS for Sunitinib received in 1st line
- OS for Sunitinib received in 1st line

ORR under Axitinib in 2nd line post Sunitinib will be given with its 2-sided 95% 'exact' Clopper-Pearson confidence interval in the SU-AXI subgroup.

Same analysis will be done for:

- CBR under Axitinib in 2nd line post Sunitinib in the SU-AXI subgroup
- ORR for Sunitinib received in 1st line
- CBR for Sunitinib received in 1st line

Additionally, following analysis will be performed according to MSKCC prognosis classification at Axitinib initiation (good/intermediate/poor) using the Kaplan Meier method:

- PFS under Axitinib in 2nd line post Sunitinib in the SU-AXI subgroup
- ORR under Axitinib in 2nd line post Sunitinib in the SU-AXI subgroup
- OS for the sequence SU-AXI in the SU-AXI subgroup
- For PFS and OS, the 3 Kaplan Meier curves corresponding to each MSKCC prognosis categories will be printed on a same graph.

Following analysis will be performed according to MSKCC prognosis classification at Sunitinib initiation (good/intermediate/poor) using the Kaplan Meier method:

- PFS for Sunitinib received in 1st line
- OS for Sunitinib received in 1st line
- ORR for Sunitinib received in 1st line
- CBR for Sunitinib received in 1st line
- For PFS and OS, the 3 Kaplan Meier curves corresponding to each MSKCC prognosis categories will be printed on a same graph.

If the number of patients who received IO in 2nd line is sufficient, following analysis will be performed according to MSKCC prognosis classification at Sunitinib initiation (good/intermediate/poor) using the Kaplan Meier method:

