8.2. Setting

The study will enroll patients according to the eligibility criteria in participating countries across Europe. The recruiting centers will be representative of each country involved in terms of care management systems, of size and of practices (at least when performing feasibility).

Any patient who meets the eligibility criteria will be invited to participate in the study with no selection by the investigators. The enrollment visit will be performed at the time of the patients' inclusion, after the patients' acceptation of enrollment in the study.

Data will come from medical records and will be collected in routine clinical practice. The enrollment visit will comprise a first section on patients' eligibility for every patient whatever pool they belong to and a second section depending on the treatment started (SU or AXI) at the inclusion.

For patients enrolled in the study when AXI is started as a 2^{nd} line therapy, a retrospective section will be completed at patients' inclusion, to collect data on SU 1^{st} line treatment.

For patients who start AXI when SU is discontinued during the study, the AXI initiation visit will resume baseline data that need to be updated.

Follow-up will be ensured during visits in the context of usual patients' care management (non-interventional study). No visits will be required by the protocol of the study. As long as the

patients are treated with SU or AXI, every visit to the center will be recorded. In accordance with ESMO guidelines and physicians clinical practice is real life, follow-up visits are approximately expected:

- during SU treatment: every 6 weeks (every cycle) with tumor assessment approximately every 3 months with respect to the clinical practice
- during AXI treatment: every 4 weeks (every cycle) with tumor approximately assessment every 2 months with respect to the clinical practice

[figure not shown]
When patients come off SU treatment (i.e. are not receiving AXI) or come off Axitinib (after receiving the SU-AXI sequence) they will be followed up every 6 months (separate form) for survival until the end of the study.

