8.7.3. Safety Analysis

Summaries and listings of AEs and other safety parameters will be provided by period of treatment (Sunitinib, Axitinib).

Frequencies of patients experiencing at least one AE will be displayed by body system and preferred term according to MedDRA terminology. Summary tables will present the number of patients observed with AEs and corresponding percentages.

The description will be conducted for all the reported AEs whether related to the drug or not, and then for the AEs related to SU or AXI.

Adverse event reported by patients through the quality of life questionnaires will also be described.

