ANNEX 3: QUALITY OF LIFE QUESTIONNAIRES

1. FKSI-19 QUESTIONNAIRE

1	Pleas	w is a list of statements that other people wit te circle or mark one number per line to it					
t	the p	ast 7 days.					
1			Not at all	A little bit	Some- what	Quite a bit	Very much
	GP1	I have a lack of energy	0	1	2	3	4
	GP4	I have pain	0	1	2	3	4
	C2	I am losing weight	0	1	2	3	4
	HI7	I feel fatigued	0	1	2	3	4
	Bl	I have been short of breath	0	1	2	3	4
	BRJM3	I am bothered by fevers (episodes of high body temperature)	0	1	2	3	4
	BP1	I have bone pain	0	1	2	3	4
	L2	I have been coughing	0	1	2	3	4
	HI12	I feel weak all over	0	1	2	3	4
	RCC	I have had blood in my urine	0	1	2	3	4
	C6	I have a good appetite	0	1	2	3	4
	GF5	I am sleeping well	0	1	2	3	4
	GE6	I worry that my condition will get worse	0	1	2	3	4
	G#2	I have nausea	0	1	2	3	4
	CS	I have diarrhea (diarrhoea)	0	1	2	3	4
	GDS	I am bothered by side effects of treatment	0	1	2	3	4
	GF1	I am able to work (include work at home)	0	1	2	3	4
.	GF3	I am able to enjoy life	0	1	2	3	4
	GF7	I am content with the quality of my life right now	0	1	2	3	4
		sesse-Ralated Symptoms Subscale – Physical					

Please inform your doctor of any adverse event you have experienced

Subject ID:

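### The by-period AE tables give crude percentages with no time at risk and pool two kinds of sunitinib AE capture, so differences between the sunitinib and axitinib columns mix drug and observation effects

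*SAP*

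**What the plan says.** SAP 8.2.1 presents AEs overall and by treatment period, in an overview and then by SOC and PT for all AEs, common AEs, serious and non-serious AEs, and grade 3 and 4 AEs; the set is repeated for related AEs. On the measure: "The tables will present the number of subjects and the rate of occurrence within each period for which the events occurred", and then "The rate of occurrence will be expressed as a percentage of the subjects from the Safety Analysis Set receiving the treatment concerned". On counting: "the same classification (SOC and / or PT) in the same patient is counted only once". The only duration item in that section is time on treatment until discontinuation for an AE. SAP 6.2.1 words the threshold for common events as more than 10% in one or other group. SAP 4.2 excludes statistical tests.

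Collection of sunitinib AEs depends on how the patient entered:
- Enrolled at sunitinib start: the sunitinib follow-up form (Annex 1, CRF 3.2) asks for adverse events since the last visit, without a causality condition.
- Enrolled at axitinib start: the retrospective section of the axitinib initiation visit (CRF 4.1) asks only for events related to sunitinib. Protocol 10.4 likewise limits retrospective reporting to events that a healthcare provider explicitly attributed to a sponsor drug. Protocol 10.5.1 drops the attribution condition for Switzerland.

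On visits, Protocol 8.2 expects "during SU treatment: every 6 weeks (every cycle) with tumor assessment approximately every 3 months", and every 4 weeks on axitinib; no visits are mandated. The quality-of-life forms are monthly and used only on axitinib, with the footer "Please inform your doctor of any adverse event you have experienced". Protocol 8.7.3 adds: "Adverse event reported by patients through the quality of life questionnaires will also be described". SAP 8.2.1 does not mention this.

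**The concern.** A percentage of patients with at least one event rises with the time each patient is observed. If patients stay longer on one drug than on the other, its column shows a higher percentage even when the event rate per month is identical. Nothing in the table would let a reader see or undo this.

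The second problem is separate. The sunitinib all-AE column has one denominator but two numerators: all events for one group of patients, attributed events only for the other. That pulls the sunitinib all-AE percentage down for reasons unrelated to the drug.

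These tables serve the secondary objective on safety and tolerability of the SU-AXI sequence. With the two periods laid out alike and a shared common-event threshold, readers will compare the columns whether or not a test is planned.

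**Working it through.** **1. Planned denominators (Protocol 8.5).** 525 x 0.68 = 357 and 357 x 0.35 = 124.95, stated as 125; 225 + 125 = 350; 225 + 525 = 750. The protocol's figures reproduce. Under the SAP's rule the sunitinib column would have about 750 patients and the axitinib column about 350. Retrospectively documented patients are 225/750 = 30% of the sunitinib column.

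**2. Effect of unequal time alone.**

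Inputs:
- Axitinib median time on drug: 6.5 months, or 4.8 as an alternative. These are the median PFS figures after sunitinib quoted in Protocol section 6 (investigator and independent review), used as a proxy.
- Sunitinib median time on drug: not in the documents; 5, 8, 11 and 14 months assumed.
- First-event hazard h: not in the documents; the same on both drugs by assumption. Times exponential.

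Formula: percentage with an event = h / (h + ln 2 / median time on drug).

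For h = 0.05 per month and axitinib at 6.5 months: 0.05 / (0.05 + 0.693/6.5) = 31.9%.

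| Assumed sunitinib median (months) | Sunitinib % | Gap to 31.9% (points) |
|---|---|---|
| 5 | 26.5 | -5.4 |
| 8 | 36.6 | +4.7 |
| 11 | 44.2 | +12.3 |
| 14 | 50.2 | +18.3 |

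The true rate is 5 per 100 patient-months in every cell. With axitinib at 4.8 months the axitinib figure is 25.7% and the gaps run from +0.8 to +24.5. With axitinib at 6.5 months, gaps run from -3.2 to +13.0 at h = 0.02 and from -6.5 to +18.5 at h = 0.10.

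**3. Effect of attributed-only capture on the percentage.** If a fraction c of retrospective patients with an AE have it recorded, the sunitinib all-AE percentage is multiplied by (525 + 225c)/750. That is 0.85 for c = 0.5 and 0.775 for c = 0.25 (both assumed). At an 11-month sunitinib median, 44.2% becomes 37.6% or 34.3%, and the gap falls from +12.3 to +5.7 or +2.4. At 8 months and c = 0.5 the gap is 31.1 - 31.9 = -0.8.

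**4. A pooled rate would inherit the same bias.** Take h = 0.05, an 11-month median and retrospective events recorded at half the true rate.
- Prospective: 525 x 0.4424 = 232.3 patients with an event, in 525/(0.05 + 0.0630) = 4,645 patient-months.
- Retrospective: 225 x 0.025/(0.025 + 0.0630) = 63.9, in 225/(0.025 + 0.0630) = 2,556 patient-months.
- Pooled: 296.2/7,202 = 4.1 per 100 patient-months, against a true 5. At a quarter of the true rate it is 269.5/7,625 = 3.5.

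Step 3 thins patients and step 4 thins the rate; both simplifications push sunitinib down.

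**5. Visit interval and questionnaire prompt.** Expected contacts per 26 weeks are 26/6 = 4.3 on sunitinib and 26/4 = 6.5 on axitinib, a ratio of 1.5. As an outer illustration only, if that ratio carried over fully to the axitinib detection rate, axitinib would show 0.075/(0.075 + 0.693/6.5) = 41.3%. The 11-month, c = 0.5 gap would then be 37.6 - 41.3 = -3.7. The sign depends on which contributors are present and how large they are.

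**The case against.** The strongest reply is that no comparison is planned. The study is non-controlled, the objective is descriptive, SAP 4.1 states no hypotheses and SAP 4.2 excludes tests. The percentage of treated patients with an event is a legitimate summary, and the SAP defines its term in the next sentence, so the word rate does not mislead. This stands in part: the fault is one of presentation and interpretation, not of inference. It does not remove the need for exposure beside percentages set out by period.

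A reader might infer that differences between the columns reflect observation rather than drug. The documents do not support that. They give no sunitinib duration and no AE frequency, so the size and even the sign of the time effect are assumed, and the contributors can act in opposite directions.

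A reader might also give weight to the 6-week against 4-week visits and to the questionnaire prompt. Both are at most secondary. The sunitinib form asks for everything since the last visit, so a longer interval leaves no period unasked. The questionnaire footer sends patients to their doctor, and SAP 8.2.1 does not bring questionnaire reports into the period tables. The FKSI treatment-side-effect subscale is already analysed separately in SAP 8.2.4, so item-level reporting would add little.

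Other planned outputs, such as Kaplan-Meier TTF on axitinib and PFS on sunitinib, give some idea of duration. They do not supply time at risk for an event. Table shells are in separate documents and may add exposure, but the SAP does not ask for it.

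**Conclusion.** The point holds as a presentation weakness that is cheap to correct. By-period AE percentages carry no time at risk, and 30% of the planned sunitinib denominator has attributed-only, retrospective capture (Swiss reporting under Protocol 10.5.1 excepted). Differences between columns mix drug and observation effects.

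Under equal hazards, exponential times and assumed sunitinib medians of 5 to 14 months, time alone gives gaps of -5.4 to +18.3 points at 5 events per 100 patient-months with axitinib at 6.5 months. Restricted capture lowers the sunitinib all-AE percentage by a factor of 0.85 or 0.775 at the assumed capture fractions. Only the 225/750 split and the difference in collection are documented; the rest is a range under assumptions, and the net direction cannot be fixed. Related-AE tables are less affected by the capture difference. No primary endpoint is touched.

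Exposure adjustment corrects unequal time, not unequal capture. A pooled all-AE sunitinib rate therefore cannot serve as a basis for comparing the periods.

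**What to change.** In SAP 8.2.1:
- Keep the crude percentages. Beside them, in each by-period table, add patient-months at risk and patients with a first event per 100 patient-months with 95% CI. Time runs from first dose in the period to first event or end of the period.
- Show the sunitinib period separately for prospectively and retrospectively documented patients. Restrict the sunitinib all-AE rate to prospective patients; pool the two groups only for related AEs.
- State which period receives events in the gap between sunitinib and axitinib, and events in the 28 days or more after the last dose that Protocol 10.1 includes in safety reporting.
- Add a caution under the tables that the periods are not directly comparable.

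Reconcile Protocol 8.7.3 with SAP 8.2.1: the protocol promises a description of AEs from questionnaires that have no AE field, and the SAP is silent on it. Also reconcile the safety question on the axitinib follow-up form (CRF 4.2), which asks about events related to sunitinib, with the axitinib tables.

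The cost is small. AE onset and the main treatment dates are already collected. The tables become longer, the rate assumes a roughly constant hazard within a period, and treatment end dates on the study discontinuation form (CRF section 6) are month and year only, so a day convention is needed.

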8.5. Study size

The primary endpoints of this study in patients with adv/mRCC are PFS and TTF for patients receiving AXI in 2nd line and the combined PFS and TTF for patients receiving the SU-AXI sequence. In this non-interventional real life study, the objective is only descriptive and the sample size will rely on the precision of the estimate.

The expected precision of the median PFS can be calculated with the Greenwood's formula. The formula provides an estimate of the variance of S(t) (Kaplan-Meier estimate) as follows:

$$\hat{Var}[\hat{S}(t)] = [\hat{S}(t)]^2 \sum_{j:t_i \leq t} \frac{d_j}{n_j(n_j - d_j)}$$

where tj is the times of events, dj the number of events at these times and nj the sample size at risk.

Assuming the absence of right-censoring before the median survival and the occurrence of a single event for each event time, Greenwood's formula for median survival can be simplified as follows:

$$\hat{Var}[\hat{S}(t)] = \frac{0, 5^2}{n}.$$

The different variances and CI of S(t) can therefore be calculated as a function of n and accuracy.

		Variance	
s(t) ²	n	$(s(t)^2/n)$	Accuracy
	150	0.001666667	0.080
	175	0.001428571	0.074
	200	0.00125	0.069
	225	0.001111111	0.065
0.25	250	0.001	0.062
	300	0.00083	0.056
	350	0.0007143	0.052

Table 2: sample size and accuracy of PFS

Inclusion of 350 patients with the SU-AXI sequence will allow demonstration of median progression free survival as well as time to treatment failure with an accuracy of 5.2%.

The SU-AXI 350-patient sample is expected to comprise two thirds of patients enrolled in the AXI 2nd line pool (approx. 225 patients) and one third of patients enrolled in the SU 1st line pool then receiving an AXI 2nd line (approx. 125 patients).

This last group (125 patients) implies initial inclusion of 525 patients in the SU 1st line pool. Based on current EU market research and 2014 forecasts, it is expected that 68% of the SU 1st line pool has a 2nd line treatment (357 patients); and that 35% are expected to initiate 2nd line treatment with AXI (125 patients).

ADONIS is therefore targeting approximately 750 patients: 225 in the AXI pool and 525 in the SU pool. These estimates will allow for an approximate SU-AXI 350- patient group to meet primary outcome objectives and a SU – other 2nd line treatment group of 230 patients to meet secondary objectives.

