5 ANALYSIS SETS/POPULATIONS

5.1 FULL ANALYSIS SET

The Full Analysis Set (FAS) refers to all eligible patients enrolled in the study, whatever the therapeutic strategy used during the observation period: i.e. patients enrolled when they start a treatment with SU in 1st line or AXI in 2nd line post SU treatment.

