The Clinical Benefit Rate (CBR) will be the proportion of patients with a CR, PR or Stable Disease as best response under Sunitinib treatment (cf. CRF page 12 for patients included at time of Sunitinib initiation, cf. CRF page 26 for patients included at time of Axitinib initiation).

OS status and OS time will be calculated as detailed below:

Variable name	Definition					
OS status	Patient will not be censored for the OS analysis (OS status = 1) in the following cases:					
	1) Death reported in Long term Follow-up (cf. CRF page 36)					
	 Death reported on the Study Discontinuation form (cf. CRF page 37) 					
	In all other cases, patient will be censored for the OS analysis (OS status $= 0$).					
OS time	The overall survival time will be calculated in months as:					
(months)	 (Date of death reported in Long term Follow-up - Start date of Sunitinib + 1) / 30.44, if case n°1 described above is reported 					
	 (Date of death reported on the Study Discontinuation form - Start date of Sunitinib + 1) / 30.44, if case n°2 described above is reported 					
	Else, the overall survival time will be censored as follows:					
	 (Maximum of {All visits dates reported} - Start date of Sunitinib + 1) / 30.44 					
	Note: Start date of Sunitinib will be the one reported :					
	- at time of Sunitinib initiation visit for patients enrolled at SU initiation (cf. CRF page 11 " Therapy started with Sunitinib in 1st line on ")					
	- at time of Axitinib initiation visit for patients enrolled at AXI initiation (cf. CRF page 26 "Therapy started with Sunitinib in 1st line on")					

- Progression Free Survival (PFS) for Sunitinib received in 1st line

PFS status and PFS time will be calculated as detailed below:

Patients included at time of Sunitinib initiation (i.e. prospective group)

Variable name	Definition
PFS status	Patient will not be censored for the PFS analysis (PFS status = 1) in the following cases:
	 Tumor Assessment showing PD in at least one Sunitinib follow- up visit (cf. CRF page 12)

Variable name	Definition					
	 2) Death within 3 months after treatment discontinuation / last Tumor Assessment. Death could be reported whether on Sunitinib discontinuation page (cf. CRF page 17) or on Study Discontinuation visit (cf. CRF page 37) 					
	In all other cases, patient will be censored for the PFS analysis (PFS status $= 0$).					
	Note: the following cases should be discussed at time of DRMs:					

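### First-line sunitinib OS and the sunitinib-period all-cause AE and death proportions pool patients enrolled at axitinib start (planned 30%), who cannot die on sunitinib and mostly contribute only attributed AEs

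*SAP*

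**What the plan says.** **Population for efficacy.** SAP 8.2.2 states that "Efficacy analyses will be provided in the FAS population". SAP 5.1 defines that set as all eligible patients whatever their route: "patients enrolled when they start a treatment with SU in 1st line or AXI in 2nd line post SU treatment". Protocol 8.7 likewise names all enrolled patients as the primary population for efficacy and safety.

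**First-line OS.** In SAP 8.2.2 the axitinib and sequence endpoints are each limited to the SU-AXI subgroup. The line "OS for Sunitinib received in 1st line" carries no such limit, and it is repeated by MSKCC group. An OS derivation table in SAP 6.1.2, printed without a heading just before first-line sunitinib PFS, takes the sunitinib start date reported "at time of Axitinib initiation visit for patients enrolled at AXI initiation". The clock for these patients therefore starts before enrolment, and no delayed entry is mentioned.

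**Safety.** SAP 8.2.1 gives AEs by treatment period: "The rate of occurrence will be expressed as a percentage of the subjects from the Safety Analysis Set receiving the treatment concerned". For deaths, "Proportion of patients who died due to any cause will be given with its 2-sided 95" per cent interval, overall and by period.

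**AE capture.** The sunitinib follow-up visit form (Annex 1, section 3.2) asks about any AE since the last visit. The retrospective sunitinib section of the axitinib initiation visit (Annex 1, section 4.1) asks only about AEs related to sunitinib. Protocol 10.4 requires explicit attribution by a healthcare provider. Protocol 10.5.1 makes an exception for Switzerland.

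**Where the routes are split.** SAP 8.2.5 and 8.2.6 split patient characteristics by enrolment route. No split is stated for OS, AEs or deaths.

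**The concern.** A patient enrolled at axitinib start has, by definition, survived first-line sunitinib and gone on to a second line. Adding such patients to a cohort followed from sunitinib start causes three problems.

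- **OS.** They carry guaranteed event-free time from sunitinib start to axitinib start, and none belongs to the group that never reaches second line. The mixture is not a cohort of sunitinib starters.
- **Deaths in the sunitinib period.** They add to the denominator and can add nothing to the numerator.
- **All-cause AEs in the sunitinib period.** One percentage mixes full capture with attributed-only capture.

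Readers would take these outputs as the real-world experience of patients starting sunitinib, overall and by MSKCC group. A preferred term could also drop out of the most-common-AE table, which has a 10% cut-off, because of how it was collected.

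**Working it through.** **Inputs from Protocol 8.5.** The target is "225 in the AXI pool and 525 in the SU pool"; "it is expected that 68% of the SU 1st line pool has a 2nd line treatment", and 35% of those are expected to receive axitinib.

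**Reproducing the plan's figures.** 125 / (0.68 × 0.35) = 525.2 (stated 525). 225 + 525 = 750. 225 + 125 = 350. Other second line: 357 − 125 = 232 (stated about 230). Precision at n = 350: 1.96 × √(0.25/350) = 5.24 points (stated 5.2%). All agree.

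**Share affected.** 225/750 = 30%. The share of patients reaching axitinib rises from 125/525 = 23.8% among sunitinib starters to 350/750 = 46.7% in the pool.

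**Deaths in the sunitinib period.** With x deaths on sunitinib, the pooled proportion is x/750 instead of x/525, a factor of 525/750 = 0.70 whatever the true rate. A true 10% is 52.5/525; pooled, 52.5/750 = 7.0%.

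**24-month OS.** Let S2 and S0 be 24-month survival from sunitinib start with and without a second line. Neither is in the documents. Assume axitinib starters survive like other second-line patients.

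- Sunitinib starters: 0.68·S2 + 0.32·S0
- Pooled: 0.70 × (0.68·S2 + 0.32·S0) + 0.30·S2 = 0.776·S2 + 0.224·S0
- Shift: 0.096 × (S2 − S0)

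| Assumed S2 − S0 | Shift (points) |
|---|---|
| −0.2 | −1.9 |
| 0 | 0 |
| 0.2 | +1.9 |
| 0.4 | +3.8 |
| 0.6 | +5.8 |

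An uncensored simulation gave +2.2 to +6.0 points at 24 months and +1.3 to +3.2 months in the median. Its inputs are assumed, not documented: median sunitinib duration 6–12 months; 5–15% dying on sunitinib; post-sunitinib medians of 3–6 months (no second line), 12–15 (other second line) and 12–20 (axitinib).

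**All-cause AEs.** Let q be the share of retrospective patients with a given AE category who still show it under attributed-only capture (not documented). Pooled incidence is the true incidence × (0.70 + 0.30q).

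| Assumed q | Factor | Relative loss |
|---|---|---|
| 0.9 | 0.970 | 3% |
| 0.75 | 0.925 | 7.5% |
| 0.5 | 0.850 | 15% |

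At q = 0.5, a term with true incidence up to 10%/0.85 = 11.8% falls below the 10% cut-off.

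The loss depends on how common the category is. If AEs per patient are Poisson with mean m and a fraction c of events is captured, q = (1 − e^(−mc)) / (1 − e^(−m)), and the loss is 0.30 × (1 − q).

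| Category | c = 0.25 | c = 0.50 | c = 0.75 |
|---|---|---|---|
| At least one AE (m = 4) | q 0.644, loss 10.7% | q 0.881, loss 3.6% | q 0.968, loss 1.0% |
| Single term, 20% incidence | q 0.271, loss 21.9% | q 0.528, loss 14.2% | q 0.771, loss 6.9% |

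**The case against.** The strongest points on the other side are these.

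- **The OS table is unlabelled and its event sources are odd.** It counts deaths from the long-term follow-up and study discontinuation forms but not from the sunitinib discontinuation page, which first-line PFS does use. That list would also fit OS for other second-line sequences. This uncertainty is real, but its position and its rule for patients enrolled at axitinib start favour the first-line reading. The pooling also follows from SAP 5.1 and 8.2.2 without this table.
- **Text nearby is incomplete, and table shells are in separate documents.** A split may exist there. The SAP nevertheless writes the split out for patient characteristics and not for these outcomes.
- **No denominator is stated for deaths.** The denominator sentence belongs to the AE tables, so its use for deaths is inferred. SAP 8.2.1 does place all safety analyses in the safety population. Every planned patient has received sunitinib, so the whole set and the sunitinib-treated set both number 750 at plan.
- **The 10% cut-off matters less than it seems.** SAP 8.2.1 also tabulates all AEs, and SAP 6.2.1 reports ten named AEs at any frequency. The related-AE tables largely avoid the capture mismatch. This softens the cut-off point; the all-cause percentages remain mixed.
- **The direction of the OS bias is not proven.** Patients without a second line may include some still doing well on sunitinib. This stands, and the sign is therefore conditional.
- **These are peripheral outputs.** First-line sunitinib OS is not a protocol objective and the study is descriptive. This limits the severity, but the SAP plans to report the figures.

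**Conclusion.** The concern holds. Followed literally, the SAP produces a first-line sunitinib OS from a cohort partly selected on survival to second line, and sunitinib-period all-cause AE and death proportions with mismatched numerators and denominators.

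The sunitinib-period death proportion is 30% too low in relative terms at planned sizes, provided deaths use the same denominator as AEs. That factor rests only on the planned split. All-cause AE incidence is too low by an amount the documents do not determine, since q is unknown. OS is too high if patients without a second line survive less well; S2, S0 and the survival of axitinib starters are all assumed. The Swiss exception slightly reduces the AE mismatch.

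Only secondary and safety outputs are affected. The primary endpoints are defined in the SU-AXI subgroup and are untouched. The change should be made, but it does not threaten the main conclusions.

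**What to change.** In SAP 8.2.1 and 8.2.2, state that first-line sunitinib OS (overall and by MSKCC group) and the sunitinib-period all-cause AE and death proportions are estimated in patients enrolled at sunitinib initiation (about 525). Show patients enrolled at axitinib start in a separate column, with related AEs only. Name the denominator for deaths by period, and give the OS table in SAP 6.1.2 a heading. Show first-line PFS, ORR and CBR by enrolment route as well; no direction of bias is claimed for these.

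Delayed entry alone is not a substitute. In the simulation it did not reliably recover the sunitinib-start value, because the added patients are selected on receiving axitinib and not only on surviving.

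The cost is a population statement and one extra column, from data already collected. Intervals become about 20% wider: √(750/525) = 1.195. By the protocol's own formula the half-width at the median is 1.96 × √(0.25/525) = 4.3 points, against 1.96 × √(0.25/750) = 3.6 points when pooled.
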